**4. Dental Plaque Accumulation in Mechanically Ventilated Adults.** In a sub-study of this R01 during its initial funding period, dental plaque data was evaluated longitudinally in a subset of the control group enrolled within 24 hours of intubation in the first year of data collection of R01 NR007652 (n=137). Subjects in the control group received usual oral care delivered by the bedside nurse; nurses were free to individualize the method of oral care, and the study units did not have protocols that specified tools and solutions for oral care. Baseline oral health status was assessed by a count of decayed, missing, and filled teeth (DMFT). Dental plaque was assessed using the UM-OHI on study days 1, 3, 5 and 7; observations were augmented by use of a dental plaque disclosing agent, visible only under ultra-violet (UV) light. This dental plaque assessment strategy was substantially more valid and reliable than our previous VAS. On the day of intubation, subjects had greater than 73% mean dental plaque coverage of tooth surfaces, and mean dental plaque remained greater than 60% through day 7, with statistical differences only between day 1 and day 7 ( $p = .03$ ). We further examined the pattern of dental plaque accumulation by location (buccal or lingual) and by tooth type (molars, premolars, canines, incisors). Dental plaque averages for the buccal (67%) and lingual (68%) surfaces were equivalent. The molars and premolar tooth types had the most dental plaque (greater than 70%) when compared to the other tooth types. These data reinforced earlier preliminary results regarding preexisting oral problems in mechanically ventilated adults, and further quantified high levels of dental plaque and DMFT scores. Further, the data indicated that usual oral care provided by bedside nurses was not effective in plaque removal.

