## Key Variables and Measurement

In this final phase of our investigation of oral care in mechanically ventilated adults, our goal is to determine optimal tooth brushing frequency. Taken as a whole, the work conducted in R01 NR007652 (the proposed project combined with the results of the previous and current projects) results in clear, complete, evidence-based guidance for nurses providing oral care to mechanically ventilated adults.

The primary aims of the proposed project are: 1) Evaluate the clinical equivalence (non-inferiority) of three tooth brushing frequencies on oral health (dental plaque and mucosal inflammation) in critically ill adults receiving mechanical ventilation; and 2) Quantify and compare the safety of three tooth brushing frequencies on serious adverse outcomes, including ventilator associated complications and clinically relevant HAIs (including VAP, bacteremia, and sepsis). A secondary aim is to investigate patient factors that influence tooth brushing frequency benefit and risk in critically ill adults.

We will accomplish these objectives using a prospective, randomized, experimental design. Subjects (n=345) will be randomly assigned within 36 hours of intubation to one of three intervention groups which differ in frequency of tooth brushing (once, twice, or three times daily). The intervention, a standardized tooth brushing protocol developed and tested in the previous project, will be delivered by study personnel for 7 days, or until extubated (if extubation occurs within the first 7 days). Key variables and their measurement intervals are presented in Table 1, and will be described more fully in the Research Design section.

Table 1: Key variables

Concept	Variable	Measurement interval
Oral Health (Specific Aim 1)	Dental Plaque: UM-OHI, augmented with DPIA	Daily for 7 days while intubated, days 1,3,5 post-extubation*
	Gingival inflammation: GCF IL-1 $\beta$	Daily for 7 days while intubated, days 1,3,5 post-extubation*
Serious outcomes (Specific Aim 2)	Systemic Inflammatory Response Syndrome criteria	Daily for 7 days while intubated, days 1,3,5 post-extubation*
	HAI: positive epidemiologic surveillance report for VAE (including VAP), bacteremia, sepsis	Daily for 7 days while intubated, days 1,3,5 post-extubation*
	Length of stay (ICU and hospital)	Calculated at hospital discharge
	Length of intubation	Calculated at time of extubation
Patient factors (Specific Aim 3)	Demographics (age, gender, smoking status)	On study admission

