	Severity of Illness: APACHE	On study admission
	Global oral health: DMFT	On study admission

\*Post-extubation data will not be collected on subjects who remain intubated beyond the 7 day intervention period.

**Oral Health: Dental Plaque.** Dental plaque will be assessed using the University of Mississippi Oral Hygiene Index (UM-OHI), with observations documented and augmented by use of a digital intraoral camera (obtaining images of every tooth at each observation for later analysis). The UM-OHI assessed prior to the first tooth brushing intervention, and daily every day for the first seven days of intubation. If extubated during the 7 day intervention period of the study, the UM-OHI will also be assessed following extubation on days 1,3 and 5 post-extubation to document resolution or persistence of dental plaque after resumption of self-administered oral hygiene. We will use dental hygienists to train study personnel to obtain the digital images, and as plaque assessors.

The UM-OHI assesses every tooth, and divides each tooth into more sections than standard tools used in dental practice, thus enhancing the ability to quantify plaque. The UM-OHI divides the oral cavity into 12 regions: left and right posterior teeth and anterior teeth in each arch, further subdivided into buccal (cheek side) and lingual (tongue side). Each tooth is divided into 5 sections for the buccal surface and 5 sections for the lingual surface. The 5 sections include the mesial, distal and middle sections (which is further subdivided horizontally into gingival, middle and occlusal sections). Each section (total of 10 for each tooth) is scored for the presence or absence of plaque. If plaque definitely exists in the section, it is scored a 1; if no plaque is present, the section receives a 0. Thus, each tooth is scored from 0 (no plaque) to 10 (plaque in every section). The mean plaque score for the subject is then calculated by dividing the total score by number of teeth.

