aTimes per day of tooth brushing. bConducted if the 1 versus 3 test of non-inferiority is not supported and  $NNH_{31}$  is between 50 to 100. NNH: number needed to harm.

Specific Aim 3, to investigate patient factors that influence tooth brushing frequency benefit and risk in critically ill adults, is considered exploratory. Repeated measures linear mixed models will be fit treating dental plaque and mucosal inflammation as separate outcome variables (transformed if required), random group assignment as a 3-level ordinal predictor variable, and a range of possible patient-level predictors. Initially, bivariate correlations for potential continuous predictors and analysis of variance (ANOVA) for potential categorical predictors will be conducted to identify potential patient factors independently associated with dental plaque and mucosal inflammation. Interaction terms between tooth brushing frequency (scored 1, 2, or 3) and individual patient factors will be constructed to assess potential effect modification. The mixed models will be fit using the normal distribution, identity link, and specifying an autoregressive correlation structure. For assessment of safety, and assuming a sufficient number of HAs for model conversion, generalized estimating equations will be fit in the same manner as the linear mixed models while specifying the binomial distribution, log link, and an autoregressive correlation structure. Through these analyses, we aim to gain insight as to specific patient factors (e.g. presenting oral health) that may modify the clinical effectiveness and safety profile associated with frequency of tooth brushing.

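### The exploratory Aim 3 mixed models name only an autoregressive correlation; fitted that way, standard errors for brushing frequency and patient factors would be too small if subjects differ lastingly

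*Combined protocol and SAP*

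**What the plan says.** All of this is in the combined protocol and SAP. Under XI. Data Analysis Plan, Specific Aim 3, the plan states: "Repeated measures linear mixed models will be fit treating dental plaque and mucosal inflammation as separate outcome variables". The predictors are "random group assignment as a 3-level ordinal predictor variable, and a range of possible patient-level predictors", and "Interaction terms between tooth brushing frequency (scored 1, 2, or 3) and individual patient factors will be constructed to assess potential effect modification". The one sentence on within-subject dependence is "The mixed models will be fit using the normal distribution, identity link, and specifying an autoregressive correlation structure". The order of the autoregression, its time index, any random effect and the type of standard error are not given. The next sentence carries the same set-up over to generalized estimating equations (GEE) for healthcare-associated infections, again with an autoregressive structure.

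Table 1 (Key Variables and Measurement) gives the schedule for both outcomes as "Daily for 7 days while intubated, days 1,3,5 post-extubation". Its footnote adds: "Post-extubation data will not be collected on subjects who remain intubated beyond the 7 day intervention period". The Aim 3 text does not say whether the post-extubation rows enter the models.

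The plan is open about the status of this work: "Specific Aim 3, to investigate patient factors that influence tooth brushing frequency benefit and risk in critically ill adults, is considered exploratory".

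**The concern.** Under AR(1), correlation fades towards zero as visits move apart. A stable subject level does not fade: two subjects with different dentition and prior hygiene may still differ on day 7 by much of what separated them on day 0. For a term that varies only between subjects, this lasting part is the component of error that more visits on the same subject cannot average away. A model without it credits repeated visits with more independent information than they carry. Randomized frequency, the patient factors and every frequency-by-factor product are of this kind.

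The documents make a lasting level plausible without sizing it. Aim 1 adjusts for baseline plaque, DMFT is recorded as preexisting oral health, and Aim 3 names presenting oral health as a possible modifier.

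At stake are the intervals and p-values of Aim 3. These models are also the only named analysis of IL-1β by arm, since the Aim 1 ANCOVA is described for plaque only, and they are where sex, race and ethnicity are to be examined. Many factors and interactions will be screened, so over-precise tests would add false leads.

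**Working it through.** **Plan's own figures.** The plan gives no standard error, within-subject correlation or power for Aim 3, so there is no Aim 3 figure to reproduce. The Aim 1 sample size does reproduce: 2(1.2816 + 1.6449)²/0.50² = 68.5, so 69 per group; 69 × 3 = 207; 207/0.60 = 345. It does not depend on the point made here.

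**Assumptions (not in the documents).** Total variance is 1. A share τ is a lasting subject level, and the remaining 1 − τ is AR(1) with lag-1 correlation ρ. The working model is AR(1) only, fitted by maximum likelihood. There are no covariates. Series lengths are 3, 4, 5, 6, 7, 7 and 7 daily rows.

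**Formulas.** On daily rows the fitted lag-1 correlation settles at r = τ + (1 − τ)ρ. For n rows the model weights the first and last row by 1/(1 + r) and each row between by (1 − r)/(1 + r). Hence:
- sum of weights: a = [n − (n − 2)r]/(1 + r)
- sum of squared weights: q = [2 + (n − 2)(1 − r)²]/(1 + r)²
- model-based variance of a between-subject mean: 1/A, with A = Σa
- true variance of the same estimate: B/A², where for ρ = 0, B = τΣa² + (1 − τ)Σq
- reported SE / true SE = √(A/B); type I error = 2Φ(−1.96 × ratio)

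**Worked case, τ = 0.5, ρ = 0 (r = 0.5).**
- a = 1.667, 2, 2.333, 2.667, 3, 3, 3, so A = 17.667 and Σa² = 46.333
- q = 1, 1.111, 1.222, 1.333, 1.444, 1.444, 1.444, so Σq = 9.0
- B = 0.5 × 46.333 + 0.5 × 9.0 = 27.667
- ratio = √(17.667/27.667) = 0.80; type I error = 2Φ(−1.566) = 11.7%

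**Range, same series lengths** (for ρ above 0, the term q is replaced by the weighted sum over the residual correlation matrix):

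| Lasting share τ | SE ratio at ρ = 0 | SE ratio at ρ = 0.5 |
|---|---|---|
| 0.3 | 0.80 | 0.93 |
| 0.5 | 0.80 | 0.92 |
| 0.7 | 0.84 | 0.93 |

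Type I error over this grid is 6.7 to 11.7%.

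**Sensitivity.**
- τ = 0: ratio 1.00, type I error 5.0%.
- Only three visits (days 0 to 2): ratio 0.94 to 1.00.
- Baseline plus seven daily visits, with a lasting component: 0.72 (τ = 0.4, ρ = 0) to 0.91 (τ = 0.2, ρ = 0.5), type I error about 7.5 to 16%.

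**Does spacing matter by itself?** Take a subject extubated on day 3 with visits on days 1, 3 and 5 afterwards (study days 0, 1, 2, 3, 4, 6, 8), no lasting component, and AR(1) counted by visit order. The ratio is 0.996 at ρ = 0.5 and 1.000 at ρ = 0.8. With τ = 0.4 and ρ = 0.3 on the same days, the ratio is 0.819 by visit order and 0.808 by actual day. Correct day indexing alone therefore does not cure the shortfall.

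**The case against.** The strongest reply is that this is missing detail, not an error. The plan calls these mixed models and does not exclude a random intercept; an intercept plus an autoregressive residual fits the text and is the remedy proposed here. A reader might infer that the plan drops stable subject differences. The documents do not establish that. Autoregressive-only is nevertheless the natural reading, because it is the only dependence named and the same set-up is carried to GEE, which has no random effects. Two analysts could follow the text and report different intervals.

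The size rests on an assumed lasting share, and this stands in full. The documents give no within-subject correlation for either outcome. Where baseline plaque or DMFT enters as a predictor, it would absorb part of the lasting variance and shrink the shortfall.

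A reader might also blame the unevenly spaced visits. That does not stand. Visits are daily during intubation, 2-day gaps arise only after extubation and only in subjects extubated within 7 days, and spacing alone moves the ratio by less than 0.5%.

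Nor does the finding in Preliminary Studies that "mean dental plaque remained greater than 60% through day 7" show within-subject stability. It is a group mean and says nothing about how subjects differ from one another, and the same study reports a day 1 to day 7 difference (p = .03).

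Finally, Aim 3 is exploratory and drives no decision rule. That stands and limits the weight of the point.

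**Conclusion.** The point holds as a conditional one. If the Aim 3 models are fitted with AR(1) alone, and if plaque or IL-1β has a lasting subject level of 30 to 70% of variance, model-based standard errors for frequency, patient factors and their interactions would be about 0.80 to 0.93 of the true value with 3 to 7 daily rows. Nominal 5% tests would then run at about 7 to 12%. The shortfall is zero without a lasting component, small with three visits, and larger with eight daily rows. How post-extubation days are indexed is a secondary specification gap. A reader might extend the point to the trial's main conclusion, but the Aim 1 ANCOVA, the sample size, the number needed to harm and the Table 2 recommendations do not use these models.

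**What to change.** Replace the sentence on correlation with a statement that:
- each mixed model has a random subject intercept plus a residual that is autoregressive in actual study day (correlation ρ to the power of days apart);
- frequency, patient factors and their interactions are reported with robust (sandwich) standard errors;
- post-extubation visits are, or are not, included.

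The sandwich errors are a safeguard: intercept variance and ρ are hard to separate in short series. If the fuller model does not converge, an autoregressive fit with sandwich errors can be the stated fallback.

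The cost is a line or two in the analysis plan and standard software options. Intervals become wider: up to about 25% in the worst case of the 3-to-7-row setting (1/0.80 = 1.25). With baseline plus seven daily visits, the standard error at τ = 0.4, ρ = 0.3 rises from 0.101 to 0.123 SD (22%), and at τ = 0.4, ρ = 0 from 0.085 to 0.117 SD (38%). If an intercept was always intended, writing it down costs nothing.

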Specific Aim 2 is to quantify and compare the safety of three tooth brushing frequencies on serious adverse outcomes, including ventilator associated complications and clinically relevant healthcare-associated infections. For aim #2, a composite HAI endpoint will be constructed consisting of VAP, bacteremia, and sepsis. Since HAIs are anticipated to be rare events across the 3 tooth brushing regimens, no formal between-group statistical testing will be conducted. Instead, 95% confidence intervals will be calculated for the proportion of subjects with HAI in each treatment arm. In addition, using person days of observation (i.e. days since intubation), we will calculate incidence rates (IR) of HAI by treatment arm and then calculate the number needed to harm (NNH) using the single daily brushing regimen as the

reference group and the formulas:  $NNH_{21} = (1 / (IR_2 - IR_1))$  and  $NNH_{31} = (1 / (IR_3 - IR_1))$  where  $IR_n$  = observed incidence rate in each treatment arm. In the event that the formal test of non-inferiority fails for the single daily brushing regimen, we will define clinically-relevant “compromised” safety as an NNH of 100 per less. This would be interpreted as 100 individuals or less being treated with the multiple daily tooth brushing to develop an HAI that otherwise would not have occurred with the single daily brushing regimen.

Clinical recommendations defined *a priori* and developed from the analyses conducted for aims 1 and 2 will be developed as defined in Table 2.

Table 2. Application of study findings to tooth brushing frequency recommendations

Comparison Groups a	Non-Inferiority	NNH	Recommendation	Rationale
1 versus 3	Supported	N/A	1 time/day	1 time/day non-inferior and safe
1 versus 3	Not supported	$\geq 100$	3 times/day	1 time/day inferior, 3 times/day safe
1 versus 3	Not supported	$< 50$	1 time/day	1 time/day inferior, but 3 times/day safety concern
1 versus 3	Not supported	50 to 100	See 1 vs. 2	1 time/day inferior, but 3 times/day safety concern
1 versus 2 b	Supported	N/A	1 time/day	1 time/day non-inferior and safe
1 versus 2 b	Not supported	$\geq 100$	2 times/day	1 time/day inferior, 2 times/day safe
1 versus 2 b	Not supported	$< 100$	1 times/day	1 time/day inferior, but 2 times/day safety concern

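### Aim 3 models healthcare-associated infection (HAI) as a serial response, so its estimates can mix the risk of acquiring an HAI with onset time and duration

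*Combined protocol and SAP*

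**What the plan says.** Section XI, Specific Aim 3: "Repeated measures linear mixed models will be fit treating dental plaque and mucosal inflammation as separate outcome variables", with brushing frequency, patient factors and their interactions as predictors. Safety follows the same pattern: "generalized estimating equations will be fit in the same manner as the linear mixed models while specifying the binomial distribution, log link". The specification ends with "log link, and an autoregressive correlation structure". The model is to be fitted only if there are enough HAIs, and Aim 3 as a whole is labelled exploratory.

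Key Variables and Measurement, Table 1, defines the variable as "HAI: positive epidemiologic surveillance report for VAE (including VAP), bacteremia, sepsis" and schedules it "Daily for 7 days while intubated, days 1,3,5 post-extubation".

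Section XI, Specific Aim 2: "a composite HAI endpoint will be constructed consisting of VAP, bacteremia, and sepsis". Two summaries are planned. One is the share of subjects with an HAI in each arm, with a 95% confidence interval. The other is a rate: "using person days of observation (i.e. days since intubation), we will calculate incidence rates (IR) of HAI by treatment arm". The number needed to harm (NNH) is the reciprocal of the difference between two arms' rates, with once-daily brushing as reference. The text interprets it as a number of individuals. Table 2 applies NNH cut-offs of 50 and 100 when non-inferiority is not supported.

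The documents do not say how days after the start of an HAI are coded, whether the rate stops at the first HAI, when time at risk ends, or how VAP, bacteremia and sepsis from one illness are counted.

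**The concern.** Plaque is a state that can be read afresh each day. An HAI is something a patient acquires. An autoregressive correlation has meaning only with several ordered responses per subject, and Table 1 supplies them, so the natural reading is a daily yes/no series. The coding after onset is open, and neither choice gives the quantity Aim 3 wants:

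- **Status stays positive.** The response is infected days. A patient factor that prolongs an infection or brings it forward looks like one that raises risk.
- **Only the onset day is positive.** There is almost no serial pattern to model, and days after the event stay in the data as if the patient could still have a first HAI.

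The same missing definition reaches Aim 2, where the rate feeds the NNH in Table 2. Overlap between components is foreseeable. The Potential Risks section describes organisms entering the bloodstream as contributing to both bacteremia and sepsis. The section on serious outcomes draws on both hospital surveillance and clinicians' diagnoses, with no rule for removing duplicates.

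**Working it through.** **1. The plan's own HAI figure.** Inputs from Statistical Power and Sample Size Justification: proportion 0.05, n = 69. Events: 0.05 × 69 = 3.45. The exact (Clopper-Pearson) interval is 0.012 to 0.131, which reproduces the stated 0.01 to 0.13. That figure uses one response per subject. At 5% of 345 subjects, 0.05 × 345 = 17.25, so about 17 subjects would have an HAI.

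**2. Daily series, status positive after onset.** The expected daily proportion is p × d / D, where p is acquisition risk, d is positive days and D is days observed. The documents give no durations or arm-specific risks, so these are assumptions: D = 7, p = 0.10 in both arms, d = 1 versus 3.

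- 0.10 × 1/7 = 0.0143 and 0.10 × 3/7 = 0.0429, an expected daily ratio of 3.0 when the risk ratio is 1.
- Simulation, 20,000 per arm:

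| Risks | Positive days | Daily ratio | Subject-level risk ratio |
|---|---|---|---|
| 10% vs 10% | 1 vs 3 | 2.89 | 0.96 |
| 10% vs 10% | 2 vs 3 | 1.51 | 1.00 |
| 10% vs 10% | 3 vs 3 | 0.98 | 0.98 |
| 5% vs 10% | 3 vs 1 | 0.66 | 1.97 |

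- A log-link binomial GEE fitted to a simulated 1,500 per arm (1 vs 3 days) gave 2.57 with independence and 2.45 with autoregressive correlation. The subject-level risk ratio in that sample was 0.092 / 0.1073 = 0.86.

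With equal durations the ratio is right, although the modelled level (about 0.043 per day) is not the risk (0.10). With unequal durations the ratio is wrong and can reverse.

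**3. Incidence rate and NNH.** Rate = p × k / D, where k is the number of times one illness is counted, and NNH = 1/(IR3 − IR1) as in Specific Aim 2. Assume D = 7 and risks of 5% (once daily) versus 10% (three times daily).

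- k = 1: 0.10/7 − 0.05/7 = 0.00714, so NNH = 140.
- k = 3: 0.30/7 − 0.15/7 = 0.02143, so NNH = 46.7.
- From subject-level proportions: 1/(0.10 − 0.05) = 20.

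In Table 2 the first value lies at or above 100, and the other two lie below 50.

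**4. Ending person-time at the event.** With 69 subjects and 7 days each: 3.45/483 = 0.0071 per day. With time ended at mid-period for those with an event: 3.45/(483 − 3.45 × 3.5) = 0.0073. The effect is small.

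**5. One extra patient under the plan's formula.** 345/3 = 115 per arm, and 115 × 7 = 805 person-days. One extra patient counted once, twice or three times gives NNH 805/1 = 805, 805/2 = 403 or 805/3 = 268. All lie at or above 100.

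**The case against.** The GEE is exploratory and conditional on enough events, and no row of Table 2 uses it. That stands, and it limits the priority.

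Daily status is an inference. A positive surveillance report can be read as an event report, and under onset-only coding a log-link model over person-days is close to a first-event rate model, with the working correlation mainly a matter of efficiency. This largely stands for that coding, except that post-event days remain at risk. It does not make the autoregressive specification coherent, and the plan does not say which coding applies. It is also true that the distortion in the ratio needs onset or duration to differ between the groups compared.

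Two stronger readings are tempting. A reader might infer that the plan prescribes counting one illness as up to three HAIs. It does not: the composite is a single endpoint, a share of subjects is also reported, and incidence ordinarily means new events. Multiple counting is left open by silence.

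A reader might also infer that one extra patient could move Table 2 through three rows, since 115 divided by 1, 2 or 3 gives 115, 58 or 38. Those divisions count subjects. The plan's formula uses person-day rates, and step 5 shows that no row changes there.

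**Conclusion.** The point holds for the Aim 3 safety model: an incident event is specified as a serial response, and neither coding of later days yields the risk of acquiring an HAI. Under assumed durations of one versus three positive days, equal risks appear as a ratio of about 2.4 to 2.9. The real size is unknown, because the documents give no durations.

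The Aim 2 part is weaker but has more bearing on the recommendations. The missing first-event and overlap rule can change the Table 2 row only under larger assumed differences, such as 5% versus 10% risk with every illness counted three times. A first-event rule alone would not suffice, because the reciprocal of a rate difference stays in person-days while the text reads it as people (140 against 20 in the same example). The planned proportion of subjects with an HAI is sound and unaffected. Overall this is a modest-priority correction.

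**What to change.** 1. Define the event as the subject's first new HAI of any component after randomisation. Count overlapping VAP, bacteremia and sepsis once, tabulate components separately, and state how an infection already present at enrolment is handled, since the exclusion criteria do not remove it.
2. For Aim 3 safety, use one row per subject: log-link Poisson regression with robust standard errors, keeping the brushing-frequency main effect and the frequency-by-factor interaction for a short pre-listed set of factors. Without an offset, label the results risk ratios. With a log(person-days at risk) offset, label them first-event rate ratios.
3. For Aim 2, use the same event in the incidence rate and end person-time at its date.
4. Compute the NNH used in Table 2 from the subject-level proportions already planned, so that its unit matches the plan's interpretation.

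The cost is SAP wording and simpler programming, with no new data, best settled before HAIs are tabulated by arm. Repeat infections would be described rather than modelled. With about 17 HAI subjects at the plan's illustrative 5%, interaction estimates will be imprecise under any model, which is why the list of factors should be short.
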